9.1.3 Intensity

The intensity assessment for a clinical AE must be completed using the following definitions as guidelines:

Assessment of Intensity	
MILD	A type of AE that is usually transient and may require only minimal treatment or therapeutic intervention. The event does not generally interfere with usual activities of daily living.
MODERATE	A type of AE that is usually alleviated with additional specific therapeutic intervention. The event interferes with usual activities of daily living, causing discomfort but poses no significant or permanent risk of harm to the research participant.
SEVERE	A type of AE that interrupts usual activities of daily living, or significantly affects clinical status, or may require intensive therapeutic intervention.
An event is defined as serious when it meets at least 1 of the predefined outcomes as described in the definition of an SAE, NOT when it is rated as severe.	

9.1.4 Assessment of Causality

Assessment of Causality	
1.	The investigator is obligated to assess the relationship between atogepant medication and each occurrence of each AE or SAE.
2.	A reasonable possibility of a relationship conveys that there are facts, evidence, and/or arguments to suggest a causal relationship, rather than a relationship cannot be ruled out.
3.	The investigator will use clinical judgment to determine the relationship.
4.	Alternative causes, such as underlying disease(s), concomitant therapy, and other risk factors, as well as the temporal relationship of the event to atogepant administration will be considered and investigated.
5.	The investigator will also consult the investigator's brochure in his/her assessment.
6.	For each AE or SAE, the investigator must document in the medical notes that he/she has reviewed the AE or SAE and has provided an assessment of causality. In evaluating causality, the investigator will need to make a Yes/No assessment (ie, related or not related) regarding a reasonable possibility that the study intervention caused the event.
7.	There may be situations in which an SAE has occurred, and the investigator has minimal information to include in the initial report to Sponsor. However, it is very important that the investigator always make an assessment of causality for every event before the initial transmission of the SAE data to Sponsor.
8.	The investigator may change his/her opinion of causality in light of follow-up information and send an SAE follow-up report with the updated causality assessment.
9.	The causality assessment is one of the criteria used when determining regulatory reporting requirements.

9.1.5 Follow-up of Adverse Events and Serious Adverse Events

After the initial AE/SAE report, the investigator is required to proactively follow each participant at subsequent visits/contacts. All AEs/SAEs and nonserious AEs of special interest (as defined in Section 6.1.2) will be followed until resolution, stabilization, the event is otherwise explained, or the participant is lost to follow-up (as defined in Section 8.8).

The investigator is obligated to perform or arrange for the conduct of supplemental measurements and/or evaluations as medically indicated or as requested by Sponsor to elucidate the nature and/or causality of the AE or SAE as fully as possible. This may include additional laboratory tests or investigations, histopathological examinations, or consultation with other healthcare professionals.

Prior to database lock, new or updated information will be recorded in the originally completed eCRF. If the event is an SAE, it will also need to be reported on the SAE reporting form. Post database lock, new or updated SAE information will only be reported on the SAE reporting form.

The investigator will submit any updated SAE data to Sponsor within 24 hours of receipt of the information.

9.2 Procedures for Reporting Adverse Events

All AEs must be recorded on the appropriate eCRF.

All AEs that are atogepant-related and unexpected (not listed as treatment-related in the current investigator's brochure) must be reported to the governing IRB/IEC as required by the IRB/IEC, local regulations, and the governing health authorities. Any AE that is marked 'ongoing' at the exit visit must be followed-up as appropriate.

9.3 Procedures for Reporting a Serious Adverse Event

Any SAE occurring during the study period (beginning with informed consent) until the EOS visit (Visit 15) or 30 days after the last dose of atogepant if the EOS visit is not done must be immediately reported but no later than 24 hours after learning of an SAE. SAEs must be reported to Sponsor as listed on the Sponsor Study Contacts Page and recorded on the SAE form. All participants with an SAE must be followed-up and the outcomes reported. The investigator must supply Sponsor and the IRB/IEC with any additional requested information (eg, autopsy reports and discharge summaries).

9.3.1 Regulatory Reporting Requirements for Serious Adverse Events

- Prompt notification by the investigator to Sponsor of an SAE is essential so that legal obligations and ethical responsibilities towards the safety of participants and the safety of a study intervention (ie, atogepant) under clinical investigation are met. For Japan, the investigator must promptly report the SAE to the head of the study center.
- Sponsor has a legal responsibility to notify both the local regulatory authority and other regulatory agencies about the safety of a study intervention (ie, atogepant) under clinical investigation. Sponsor will comply with country-specific regulatory requirements relating to safety reporting to the regulatory authority, IRBs/ IECs, and investigators. For Japan, the head of the study center must also be informed.

- Investigator safety reports must be prepared for SUSARs according to local regulatory requirements and Sponsor policy and forwarded to investigators as necessary.
- An investigator who receives an investigator safety report describing an SAE or other specific safety information (eg, summary or listing of SAEs from Sponsor) will review and then file it along with the investigator's brochure and will notify the IRB/IEC, if appropriate according to local requirements.

9.4 Exposure to Study Intervention During Pregnancy

Details of all pregnancies in female participants and female partners of male participants will be collected after the start of atogepant and until the EOS visit (Visit 15) or 30 days after the last dose of atogepant if the EOS visit is not done. Study center personnel must report every pregnancy on the Pregnancy Form (within 24 hours of learning of the pregnancy to the Serious Adverse Event Reporting Fax Number[s]: [contact] [back-up [contact]], email: [contact]), even if no AE has occurred. The pregnancy must be followed to term and the outcome reported by completing a follow-up Pregnancy Form. Abnormal pregnancy outcomes (eg, spontaneous abortion, fetal death, stillbirth, congenital anomalies, ectopic pregnancy) are considered SAEs. Elective abortions can be SAEs or AEs depending on the reason for the elective abortion (eg, fetal death, still birth, congenital anomalies, ectopic pregnancy, which would make the elective abortion an SAE). For pregnancy-related SAEs, in addition to the Pregnancy Form, a separate SAE Form must be filed as described in Section 9.3 with the appropriate serious criterion (eg, hospitalization) indicated.

9.5 ALT or AST Elevations

A treatment-emergent ALT $\geq 3 \times$ ULN and/or AST $\geq 3 \times$ ULN is considered an AESI. Any participant with this laboratory result after atogepant was taken must have repeat testing within 48 to 72 hours to confirm the abnormality. For this repeat testing, the following laboratory tests must be performed: hematology and chemistry panels, INR, serum acetaminophen level, urine drugs of abuse screen, and blood alcohol level. A blood serology sample must be collected and sent to the central laboratory for further diagnostic testing at a later date, if needed. In addition, the investigator will perform a complete history and examination to evaluate the participant for possible liver disease.

All AESIs must be reported to Sponsor within 24 hours of the time the investigator becomes aware of the event using the abnormal liver function reporting form and the AE eCRF. All new

elements of history, physical examination, diagnostic testing results, and other relevant medical reports are to be reported for each AESI.

If an ALT or AST $\geq 3 \times$ ULN is confirmed, close medical follow-up is required:

For these participants, the following laboratory tests must be performed: anti-hepatitis A IgM, hepatitis B surface antigen, anti-hepatitis B core IgM, hepatitis C antibody, hepatitis C quantitative RNA by polymerase chain reaction, anti-hepatitis E IgM, anti-hepatitis E IgG, Cytomegalovirus IgM antibody and Epstein-Barr Virus IgM antibody. The participant must be followed clinically and further medical evaluation (for other causes of acute hepatic injury) should be done per the judgment of the investigator and in conjunction with Sponsor medical personnel. In general, the chemistry panel should be repeated 1 to 2 times per week to follow the course of ALT/AST elevation.

Atogepant must be discontinued if any of the following criteria are met:

- ALT or AST $\geq 3 \times$ ULN and the participant is symptomatic with the appearance of fatigue, nausea, vomiting, right upper quadrant pain or tenderness, fever, rash, or eosinophilia ($> 5\%$)
- ALT or AST $\geq 3 \times$ ULN and total bilirubin $> 2 \times$ ULN
- ALT or AST $\geq 3 \times$ ULN and INR > 1.5
- ALT or AST $\geq 5 \times$ ULN for more than 2 weeks
- ALT or AST $\geq 8 \times$ ULN

The participant may be rechallenged with atogepant only after consultation with the Sponsor Medical Monitor. For participants who are not rechallenged, the participant should be discontinued from the study and complete an ET visit and an EOS Visit 4 weeks later. Participants should receive appropriate follow-up as per standard of care.

The investigator must contact the Sponsor Medical Monitor to discuss all cases of confirmed ALT/AST elevation $> 3 \times$ ULN. All ALT/AST elevations must be followed until ALT and AST return to $< 1.5 \times$ ULN and there is full clinical resolution.

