3.3 Adjudication Committee

An Adjudication Charter will be established and will describe the process for the surveillance, monitoring, and adjudication by the external Clinical Adjudication Committee of events of post-treatment elevations of ALT and/or AST $\geq 3 \times$ ULN. The purpose of this charter will be to provide a standardized process for the adjudication of the events in order to determine whether the elevation was related to atogepant.

4 Study Population and Entry Criteria

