6.1.2 Adverse Events of Special Interest

Selected nonserious and serious adverse events are AESIs and will require immediate reporting, recording and follow-up. The following events will be closely monitored:

- Treatment-emergent suicidal ideations with intent, with or without a plan (ie, Type 4 or 5 on the C-SSRS) or any suicidal behaviors

- Treatment-emergent elevated ALT or AST laboratory value that is $\geq 3 \times$ ULN
- Potential Hy's law cases: elevated ALT or AST laboratory value that is $\geq 3 \times$ ULN and an elevated total bilirubin laboratory value that is $\geq 2 \times$ ULN and, at the same time, an alkaline phosphatase laboratory value that is $< 2 \times$ ULN.

Reporting requirements for ALT or AST elevations and potential Hy's law cases are outlined in Sections 9.5 and 9.5.1. Responses to the C-SSRS that meet the above criterion will be captured in the eTablet and monitored by Sponsor. These AEs or events determined to be SAEs must be reported appropriately via the designated eCRFs and safety forms.

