9.5.1 Potential Hy's Law Cases

Sites must report every participant who meets the following potential Hy's law criteria if this occurs within the time the participant signs the ICF until 30 days after the last dose of atogepant:

- ALT or AST $\geq 3 \times$ ULN **AND**
- Total bilirubin $\geq 2 \times$ ULN **AND**
- Alkaline phosphatase $< 2 \times$ ULN

Study site personnel must report every participant who meets these criteria. Typically, all 3 analytes will be obtained from the same sample, but they may come from multiple samples taken within a 24-hour period. This requirement applies from the time the participant signs the ICF for the study until 30 days after the final protocol-defined study visit or the last known dose of atogepant (if the final visit does not occur).

A laboratory alert for possible Hy's law cases will be in place and must notify investigators and Sponsor immediately when the above criteria have been met. A possible Hy's law case must be faxed to Sponsor on an abnormal liver function reporting form as soon as possible (within 24 hours of learning of the possible Hy's law case) to the SAE/Pregnancy fax number, even if no AE has occurred. If the event is serious, please complete the AESI/SAE form. The eCRF for possible Hy's law cases must be completed within 7 calendar days. Every effort to determine the cause of the liver enzyme abnormalities must be made, and close monitoring should be initiated in conjunction with the Medical Monitor and Medical Safety Physician and in accordance with the FDA Guidance for Industry, Drug-Induced Liver Injury: Premarketing Clinical Evaluation, July 2009. The participant should return to the study site and be evaluated as soon as possible, preferably within 48 hours from the time the investigator becomes aware of the abnormal results. This evaluation should include laboratory tests, detailed history, and physical assessment.

10 Administrative Items

This protocol is to be conducted in accordance with the applicable GCP regulations and guidelines (eg, the ICH Guideline on GCP).

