### 6.3.7.3. Criteria for Hepatic Laboratory Abnormalities

**Table 6-4 Criteria for Hepatic Laboratory Abnormalities**

Laboratory Parameter	Categories
ALT	$\geq 1 \times \text{ULN}$
	$\geq 1.5 \times \text{ULN}$
	$\geq 2 \times \text{ULN}$
	$\geq 3 \times \text{ULN}$
	$\geq 5 \times \text{ULN}$
	$\geq 10 \times \text{ULN}$
	$\geq 20 \times \text{ULN}$
AST	$\geq 1 \times \text{ULN}$
	$\geq 1.5 \times \text{ULN}$
	$\geq 2 \times \text{ULN}$
	$\geq 3 \times \text{ULN}$
	$\geq 5 \times \text{ULN}$
	$\geq 10 \times \text{ULN}$
	$\geq 20 \times \text{ULN}$
ALT or AST	$\geq 1 \times \text{ULN}$
	$\geq 1.5 \times \text{ULN}$
	$\geq 2 \times \text{ULN}$
	$\geq 3 \times \text{ULN}$
	$\geq 5 \times \text{ULN}$
	$\geq 10 \times \text{ULN}$
	$\geq 20 \times \text{ULN}$
Bilirubin Total	$\geq 1 \times \text{ULN}$
	$\geq 1.5 \times \text{ULN}$
	$\geq 2 \times \text{ULN}$
	$\geq 3 \times \text{ULN}$
	$\geq 5 \times \text{ULN}$
	$\geq 10 \times \text{ULN}$
	$\geq 20 \times \text{ULN}$
Alkaline Phosphatase	$\geq 1 \times \text{ULN}$
	$\geq 1.5 \times \text{ULN}$
	$\geq 2 \times \text{ULN}$
	$\geq 3 \times \text{ULN}$
	$\geq 5 \times \text{ULN}$
	$\geq 10 \times \text{ULN}$
	$\geq 20 \times \text{ULN}$
Concurrent Elevations a	ALT or AST $\geq 3 \times \text{ULN}$ and Bilirubin Total $\geq 1.5 \times \text{ULN}$
	ALT or AST $\geq 3 \times \text{ULN}$ and Bilirubin Total $\geq 2 \times \text{ULN}$
Potential Hy's Law a	ALT or AST $\geq 3 \times \text{ULN}$ and Bilirubin Total $\geq 2 \times \text{ULN}$ and ALP $< 2 \times \text{ULN}$

ALT alanine aminotransferase; AST aspartate aminotransferase; TBL total bilirubin; ALP alkaline phosphatase;  
 ULN upper limit of normal (value provided by the laboratory)

a. Elevations are from the same day.

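### Three liver-safety rules in Protocol 9.5 and 9.5.1 disagree with the plan's own definitions: two at a single threshold value, and one on when Hy's law reporting ends

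*Protocol*

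**What the plan says.** **Stopping.** Protocol 9.5 lists five mandatory discontinuation criteria. One is "ALT or AST $\geq 3 \times$ ULN and total bilirubin $> 2 \times$ ULN". Protocol 6.1.2 defines potential Hy's law with "an elevated total bilirubin laboratory value that is $\geq 2 \times$ ULN", and 9.5.1 has the same inclusive limit ("Total bilirubin $\geq 2 \times$ ULN AND"). SAP 5.4.4.1 and the last row of SAP Table 6-4 also include 2 × ULN.

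**Medical Monitor contact.** Protocol 3.3 sends to adjudication "events of post-treatment elevations of ALT and/or AST $\geq 3 \times$ ULN". Sections 6.1.2 and 9.5 use the same inclusive limit to define the AESI, and 9.5 uses it to trigger repeat testing and close follow-up once confirmed. Section 9.5 then says: "The investigator must contact the Sponsor Medical Monitor to discuss all cases of confirmed ALT/AST elevation $> 3 \times$ ULN".

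**Reporting period.** Section 9.5.1 first requires reporting of a case that occurs "within the time the participant signs the ICF until 30 days after the last dose of atogepant". Later in the section the same requirement is said to run to 30 days after the last visit that the protocol defines. The last known dose becomes the reference only if that visit does not take place.

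All of this is current text. None of it comes from an amendment summary, and the amendment summaries give no reason for the differences.

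**The concern.** Safety is the primary objective (Protocol 3.1), and liver events have AESI status and external adjudication. These are rules that sites carry out as written. A mandatory stopping list should not leave out a case that the same protocol calls potential Hy's law. The omission also carries into Protocol 8.9, where the liver-related withdrawal rule refers back to the criteria in 9.5.

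The second mismatch gives one pathway two limits, so a confirmed value can be an AESI and go to adjudication without the explicit duty to call the Medical Monitor. The third leaves a site unable to tell from 9.5.1 alone whether a case found in the weeks after Day 30 must be reported under that section.

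**Working it through.** There is no sample-size, power or error-rate figure to reproduce. The check compares the inequality signs and does the date arithmetic.

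**1. Bilirubin limit.** The stopping criterion and the Hy's law definition differ only at exactly 2 × ULN. Can that value be reported? SAP Table 6-1 reports total bilirubin in mg/dL to one decimal. SAP Table 6-2 shows a ULN of 18.81 µmol/L (1.1 mg/dL). That table is a layout example, so this ULN is an assumption.

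- Conversion: 18.81 / 1.1 = 17.1 µmol/L per mg/dL. The other example values, 6.84 and 5.13 µmol/L, equal 0.4 and 0.3 mg/dL, so they lie on a 0.1 mg/dL grid.
- Limit: 2 × 1.1 = 2.2 mg/dL; 2 × 18.81 = 37.62 µmol/L.

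| Bilirubin (mg/dL) | Multiple of ULN | Stopping limit (> 2 ×) | Hy's law limit (≥ 2 ×) |
|---|---|---|---|
| 2.1 | 1.91 | not met | not met |
| 2.2 | 2.00 | **not met** | **met** |
| 2.3 | 2.09 | met | met |

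One reportable value is affected. Above 2 × ULN the stopping criterion is broader than Hy's law, because it has no alkaline phosphatase condition. The gap therefore runs one way, at equality only.

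**2. Transaminase limit.** SAP Table 6-1 reports ALT and AST in whole U/L. With a whole-number ULN, one value is an AESI without the explicit Medical Monitor duty. The documents give no ULN. For assumed ULNs of 33, 40 and 45 U/L the value is 99, 120 and 135 U/L. Over an assumed range of 30 to 45 U/L it runs from 90 to 135 U/L.

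**3. Reporting end date.** Inputs from Protocol Table 1: Week 52 is Day 364, and Visit 15 is Day 392 with a window of ± 3 days. The last dose is taken as Day 364.

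- Visit 15 after the last dose: 392 − 364 = 28 days, range 25 to 31.
- First sentence ends at last dose + 30.
- Later sentence ends at Visit 15 + 30: 28 + 30 = 58, range 25 + 30 = 55 to 31 + 30 = 61.
- Difference: 58 − 30 = 28 days, range 25 to 31.

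| | First sentence | Later sentence |
|---|---|---|
| Days after last dose | 30 | 58 (55 to 61) |
| Study day | 394 | 422 (419 to 425) |

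If Visit 15 is not done, the two statements agree. If it is done, a Visit 15 sample can fall between them only when drawn on Day 31 after the last dose (31 > 30). Table 1 schedules no laboratory test after Visit 15, so any other sample in the gap is unscheduled. An example is follow-up of an elevation that has not yet resolved, which 9.5 requires.

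**The case against.** The strongest reply is that other provisions already cover these gaps, and most of that stands.

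**Thresholds.** At exactly 2 × ULN bilirubin, a participant may still meet another criterion in 9.5: symptoms, INR above 1.5, ALT/AST at or above 5 × ULN for more than two weeks, or at or above 8 × ULN. Section 9.5.1 requires close monitoring with the Medical Monitor, and 8.9 allows withdrawal on the investigator's judgment. At exactly 3 × ULN, 9.5 already calls for evaluation together with Sponsor medical staff. A reader might infer that the protocol keeps potential Hy's law cases on drug. It does not say so. One criterion misses one value, and the documents give no frequency for it.

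**End date.** A reader might infer that a site following the first sentence would fail to report a Day 31 case that the SAP counts. The documents do not support this:

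- Every potential Hy's law case includes ALT or AST at or above 3 × ULN, which is itself an AESI. "All AESIs must be reported to Sponsor within 24 hours of the time the investigator becomes aware of the event", on the same liver form that 9.5.1 uses.
- Protocol 9.1.1 collects AEs through Visit 15. SAP 5.4.3 treats events as treatment-emergent to the later of Visit 15 and 30 days after the last dose.
- The laboratory alert in 9.5.1 notifies both the investigator and the Sponsor.
- The SAP 5.4.4.1 summary is built from blood-draw values, so a site's reading of the reporting period cannot change it.

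Nor are all participants with a Visit 15 affected in practice. The conflict matters only for someone who meets the criteria after Day 30.

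**EOS timing.** A reader might also see a conflict between the EOS visit 4 weeks after ET in 9.5 and the last-dose anchor in 5.6 and 8.8. The two agree when ET takes place at discontinuation, so no contradiction is shown.

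What the reply does not do is reconcile the text. Backstops limit the consequence, but they do not explain why one pathway has two limits or one duty two end dates.

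**Conclusion.** The three inconsistencies are real and the point holds as a minor wording correction. The first two affect one reportable value each. This rests on the reporting precision in SAP Table 6-1, the layout-example bilirubin ULN and assumed whole-number transaminase ULNs. The third is a 28-day difference (25 to 31) in a stated duty, assuming Visit 15 is held in its window. Its practical reach is limited to potential Hy's law cases arising after Day 30 from the last dose.

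No missed report, safety harm or changed SAP count has been shown, and neither the sample size nor any efficacy analysis is affected. Confidence in the textual mismatches is high.

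**What to change.** 1. In the 9.5 stopping criterion, change the bilirubin limit to ≥ 2 × ULN.
2. In the 9.5 Medical Monitor sentence, change the limit to ≥ 3 × ULN.
3. State one end date in 9.5.1. The default should be the later sentence: 30 days after the final protocol-defined visit, or after the last known dose if that visit does not occur. A site that follows it satisfies both sentences as they stand. The AE, SAE and pregnancy periods end at Visit 15 when that visit is done, so the sponsor could choose another single date, but it should state only one.

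The cost is a few words in an amendment or clarification letter. There are no new visits, tests or analyses, and item 3 by default asks nothing beyond what 9.5.1 already requires.

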9.5.1 Potential Hy's Law Cases

Sites must report every participant who meets the following potential Hy's law criteria if this occurs within the time the participant signs the ICF until 30 days after the last dose of atogepant:

- ALT or AST $\geq 3 \times$ ULN **AND**
- Total bilirubin $\geq 2 \times$ ULN **AND**
- Alkaline phosphatase $< 2 \times$ ULN

Study site personnel must report every participant who meets these criteria. Typically, all 3 analytes will be obtained from the same sample, but they may come from multiple samples taken within a 24-hour period. This requirement applies from the time the participant signs the ICF for the study until 30 days after the final protocol-defined study visit or the last known dose of atogepant (if the final visit does not occur).

A laboratory alert for possible Hy's law cases will be in place and must notify investigators and Sponsor immediately when the above criteria have been met. A possible Hy's law case must be faxed to Sponsor on an abnormal liver function reporting form as soon as possible (within 24 hours of learning of the possible Hy's law case) to the SAE/Pregnancy fax number, even if no AE has occurred. If the event is serious, please complete the AESI/SAE form. The eCRF for possible Hy's law cases must be completed within 7 calendar days. Every effort to determine the cause of the liver enzyme abnormalities must be made, and close monitoring should be initiated in conjunction with the Medical Monitor and Medical Safety Physician and in accordance with the FDA Guidance for Industry, Drug-Induced Liver Injury: Premarketing Clinical Evaluation, July 2009. The participant should return to the study site and be evaluated as soon as possible, preferably within 48 hours from the time the investigator becomes aware of the abnormal results. This evaluation should include laboratory tests, detailed history, and physical assessment.

10 Administrative Items

This protocol is to be conducted in accordance with the applicable GCP regulations and guidelines (eg, the ICH Guideline on GCP).

